Practice-Based Research Network (hereafter, the Network) dentists and dental therapists practicing in public health clinics, community health centers, Department of Veterans Affairs (VA) dental services and other dental practice types, who provide some restorative dental treatment. The purpose is to obtain information regarding their treatment practices for managing deep carious lesions and to assess their ability and willingness to participate in a randomized clinical trial (RCT) evaluating

deep caries removal strategies.

Objectives and Outcome Measures:

The primary objectives are 1) to determine eligible Network dentists' and dental therapists' current use of selective caries removal; and 2) quantify the level of concordance between their reported clinical practice and published recommendations by the International Caries Consensus Collaboration (ICCC).

The secondary objectives are to determine the ability and willingness of eligible Network dentists and dental therapists to participate in a RCT evaluating outcomes of selective *versus* non-selective (complete) caries removal for deep lesions in permanent teeth (adults 18+ years).

Outcome measures will be assessed by an electronic questionnaire regarding current clinical practice when treating deep carious lesions in permanent teeth and the dentists' and dental therapists' ability and willingness to participate in an RCT evaluating outcomes of deep caries removal strategies.

Population: The study population will include a stratified random sample. A

> census of eligible Network dentists and dental therapists practicing in public health clinics, community health centers and VA dental services will be taken. A random sample of eligible Network dentists and dental therapists from other dental practice types will be invited to participate, using a randomized denominator file. A minimum sample size of 385

respondents will be obtained.

Number of Sites: NA

Study Duration: 9 months

DCRS-Protocol-2021-02-22-V2.0

Subject Participation Duration: One-time completion of online questionnaire (approximately 15 minutes). Approximately 40 participants will complete the online questionnaire a second time for the purposes of establishing test-retest reliability.

Estimated Time to Complete Enrollment:

3 months

Schematic of Study Design:

Phase 1

- Enrollment of new dentists into the Network from public health clinics, community health centers and VA dental services
- As of June 19, 2020, of total enrollees (7,859) in the Network, only 0.03% are dentists from public health practices, community health centers or VA dental services.

Recruitment of practitioners into the study

- Eligible dentists and dental therapists from public health clinics, community health centers, VA dental services, and other dental practice types
- Email notification and invitation to participate with link to web-based questionnaire
- Informed consent will be tacitly inferred after the practitioner has read the information sheet, which will be the first page of the questionnaire

Retest of the questionnaire

40 practitioners that completed questionnaire will be selected to participate

Phase 3

Phase 2

Data analyses

Merging study questionnaire data with Enrollment Questionnaire

Phase 4

Dissemination of findings

- Manuscript submission to peer-reviewed journal
- Webinar presentations

2 INTRODUCTION: BACKGROUND INFORMATION AND SCIENTIFIC RATIONALE

2.1 Background Information

Dental caries remains a significant challenge for older Americans (1,2) and worldwide (3). The Global Burden of Disease 2015 study found a 45% increase in years lived with disability due to untreated caries in permanent teeth from 1990 to 2015 (3). Globally, untreated caries in permanent teeth ranked as the most prevalent condition evaluated (34% age-standardized), affecting 2.5 billion people (3). The expectation is that untreated caries will continue to rise in the US as the aging population increases and the edentulous rate decreases. In treating dental caries, the objective is to control disease activity and preserve hard tissue while restoring the tooth to normal form and function. Current evidence suggests that less invasive treatment should be employed, and the ICCC has published recommendations on carious lesion terminology and recommendations on carious tissue removal (4,5). These recommendations include treating cavitated carious lesions in a manner that preserves hard tissue and retains teeth long-term. The recommended priorities include preserving healthy and remineralizable tissue, achieving good restorative seal, maintaining pulpal health, and maximizing restoration success. Furthermore, the recommendations state that caries removal in shallow lesions should aim to provide a cavity able to support the final restoration, and, in deeper lesions, the priority is to maintain pulpal health (5). Specifically, teeth presenting with shallow or moderately deep cavitated carious lesions should have the carious tissue removed according to selective removal to firm dentine, while in deep cavitated lesions, selective removal to soft dentine is preferred, with more carious tissue retained selectively over the pulp (5). The FDI World Dental Federation policy on minimally invasive dentistry (2017) supports these recommendations (6). Although the American Dental Association (ADA) recently issued clinical practice guidelines on nonrestorative treatments for carious lesions (7), no clinical practice guidelines have been issued by the ADA regarding selective versus complete (nonselective) caries removal.

There is global disparity in the management of deep carious lesions. A survey of dentists in France, Germany and Norway found that 84% of Norwegian dentists employed the more conservative stepwise removal of dental caries from deep lesions, while the majority of French and German dentists (>66%) performed complete caries excavation, even for deep lesions (8). A nationwide survey (9) of US general dentists, pediatric dentists and endodontists showed that most endodontists (68%) and general dentists (47%) practiced complete caries removal, while pediatric dentists (31%) were more likely than both general dentists (12%) and endodontists (4%) to employ partial caries removal. A systematic review of seven randomized controlled trials comparing selective *versus* non-selective caries removal in children and adolescents found the risk of pulpal exposure significantly reduced in the selective caries removal group (OR=0.11, 95% CI: 0.04-0.30); while no significant difference in pulpal symptoms (OR=0.79, 95% CI: 0.30-2.12) and failure (technical or biological complications needing intervention) (OR=1.40, 95% CI: 0.69-2.84) was found between the two groups (10).

2.2 Rationale

Despite the current evidence that supports selective caries removal and that complete (non-selective) caries removal is no longer the standard of care (11-14), dentists are still apprehensive regarding the technique. A systematic review and metaanalysis (15) of dentists' management of deep carious lesions in permanent teeth found that approximately half of dentists rejected evidence-based carious tissue removal strategies. This review found that younger dentists and those in practice settings where professional guidelines were available tended to be more conservative when treating deep carious lesions. This study also noted that male dentists tended to be more invasive with caries removal techniques than female dentists. A recent study exploring teaching practices at US dental schools regarding carious tissue removal during cavity preparations found noticeable differences in management of deep carious lesions (16). An additional complication is that "caries remaining at cavity preparations" is a critical error on US dental licensure exams (16). It is therefore not surprising to observe the reluctance of US dentists to adopt more minimally invasive caries management procedures. A PEARL network study found US dentists tend to prefer nonselective caries removal to hard dentine even in the presence of anticipated pulpal exposure (17).

Dental caries is a preventable disease; however, it still affects large numbers of people globally (3) and in the US (1,2). Data from the US National Health and Nutrition Examination Survey 2011-2012, found that 27% of adults aged 20-64 years old had untreated tooth decay. Variation was observed according to race and ethnicity and higher rates were observed for non-Hispanic blacks (42%) and Hispanics (36%) compared to non-Hispanic whites (22%) and non-Hispanic Asians (17%) (2). Furthermore, rates of untreated dental caries among all age groups (children ages 5 to 18; adults ages 19 to 64; adults ages 65+) are highest for those with the lowest income (<100% federal poverty level) (18). According to a survey conducted by the ADA in 2015, 59% of adults indicated that they forgo dental care due to cost, 22% because they are afraid of the dentist and 19% because they cannot find a convenient location or appointment time (19).

This study is a cross-sectional questionnaire of Network dentists and dental therapists from public health clinics, community health centers, VA dental service and other dental practice types to determine their current use of selective caries removal; quantify the level of concordance between their reported clinical practice and published recommendations by the ICCC; and determine their ability and willingness to participate in a randomized clinical trial that could complement and extend the generalizability of the Selective Caries Removal In Posterior Teeth (SCRIPT) trial currently underway in the United Kingdom (20).

2.3 Potential Risks and Benefits

2.3.1 Potential Risks

This study poses no more than minimal risk to study participants. There are no anticipated physical, psychological, social, legal, economic, or any other anticipated risks to study participants. Study participation is completely voluntary, and participants may discontinue participation at any time without penalty or negative consequences. As

DCRS-Protocol-2021-02-22-V2.0

with any study, there is the potential for loss of confidentiality; however, appropriate precautions will be taken to mitigate this risk. These precautions include the use of unique study codes for participants and password-protected computers and secure networks for data storage. Compliance with all Institutional Review Board (IRB) regulations concerning data collection, data storage, and data destruction will be strictly observed. Data will only be accessible to research study personnel and will be stored and coded according to OHRP guidelines.

2.3.2 Potential Benefits

There are no direct benefits to the dentists and dental therapists participating in this study; however, this study will contribute to generalizable knowledge concerning selective *versus* non-selective caries removal in permanent teeth. In particular, the data collected will help explore the extent to which dentists and dental therapists are following published recommendations by the ICCC regarding carious tissue removal. Furthermore, analysis of study results will be used to support the decision regarding whether to proceed with a clinical trial. If the decision is to proceed, then it will be determined whether an efficacy trial of the intervention (selective caries removal) or an implementation study should be conducted within the Network.

3 OBJECTIVES AND OUTCOME MEASURES

3.1 Primary

Objective	Brief Description/Justification of Outcome Measure	Outcome Measured By	Time Frame
The primary objectives are to determine participating Network dentists' and dental therapists' current use of selective caries removal and quantify the level of concordance between their reported clinical practice and published recommendations by the ICCC.	Despite current evidence that supports selective caries removal as the standard of care, a recent systematic review and meta-analysis found that approximately half of dentists rejected evidence-based carious tissue removal strategies. Concordance with published recommendations will be assessed as choosing option 1 (remove all caries at the periphery of the cavity and stop before the pulp is exposed) as concordant with guidelines.	The primary outcome measures will be assessed by an electronic questionnaire regarding current clinical practice when treating deep carious lesions in permanent teeth. Level of concordance will be measured as percentage of time option 1 is chosen.	Administration of an electronic questionnaire will be used to measure this outcome.

3.2 Secondary

Objective	Brief Description/Justification of Outcome Measure	Outcome Measured By	Time Frame
The secondary objectives are to determine the ability and willingness of participating Network dentists and dental therapists to participate in a Randomized Clinical Trial (RCT) evaluating outcomes of selective versus non-selective (complete) caries removal for deep lesions in permanent teeth (adults 18+ years).	Currently there is a pragmatic, primary dental care, multi-center, two-arm patient randomized clinical trial underway in the United Kingdom with the aim of comparing the clinical and cost-effectiveness of selective caries removal with complete caries removal in permanent teeth (SCRIPT). An RCT conducted in the Network could complement and extend the generalizability of the SCRIPT trial.	The secondary outcome measures will be assessed by responses provided to an electronic questionnaire regarding the dentists' and dental therapists' ability to recruit patients with deep carious lesions extending to inner 1/3 of dentin; their willingness to participate in an RCT; and their views on outcomes that should be recorded in such a trial.	Administration of an electronic questionnaire will be used to measure this outcome.

DCRS-Protocol-2021-02-22-V2.0

4 STUDY DESIGN

This study is a cross-sectional questionnaire of Network dentists and dental therapists practicing in public health clinics, community health centers, VA dental services and other dental practice types across the United States. These practice types were chosen as they are more likely to treat patients with a higher prevalence and incidence of dental caries.

The study population will include a stratified random sample. A census of eligible Network dentists and dental therapists practicing in public health clinics, community health centers and VA dental services will be taken. A random sample of eligible Network dentists and dental therapists from other dental practice types will be invited to participate, using a randomized denominator file. At the end of the first wave of recruitment the study team will review the response rate based on EQ practitioner criteria, and may refine the sampling approach for wave 2 recruitment at that time. A minimum sample size of 385 respondents will be obtained.

Eligible Network dentists and dental therapists as described in the previous paragraph will be sent an email invitation to participate in the questionnaire study. This may be done in two or more waves depending on the numbers of eligible participants and on the response rate. The questionnaire will take approximately 15 minutes to complete and will be administered using the Electronic Data Capture System (EDC) on the Network HUB website, housed at the Network Coordinating Center (NCC).

Following the launch of the questionnaire, approximately 40 of the initial survey responders will be selected to complete the electronic questionnaire again (approximately 2 weeks post initial questionnaire completion) to establish test-retest reliability.

Approximately 3 months are estimated to complete recruitment into the study to obtain the desired sample size.

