6.2 Phase 2, Part A – Recruitment of Practitioners into the Study

- Eligible dentists and dental therapists will be identified from responses to the Network Enrollment Questionnaire and will be invited to participate based on inclusion criteria.
- A stratified random sample will be taken. A census of Network dentists and dental
 therapists practicing in public health clinics, community health centers and VA dental
 services will be taken. A random sample of eligible dentists and dental therapists
 from other dental practice types will be invited to participate, using a randomized
 denominator file.
- Agreement to complete the questionnaire will indicate that study participants have read the consent information, and this will imply tacit consent. A waiver of signed consent will be requested from the IRB.

Phase 2, Part B- Retest of the Questionnaire

- Dentists and dental therapists selected from among those study participants who completed the questionnaire will be emailed a second online questionnaire request approximately two weeks after the receipt of their first completed questionnaire.
- Dentists and dental therapists will be informed they have approximately two weeks
 to respond to the invitation to complete the retest. If the retest is not completed
 within the approximate two-week time frame, the link to the retest questionnaire will
 be disabled. A new potential retest participant will be selected from those having
 already completed the questionnaire until a total of approximately 40 retests have
 been completed.
- Completion of the retest questionnaire will indicate implied consent.

6.3 Phase 3 – Merging Study Questionnaire with Enrollment Questionnaire and Completion of Data Analyses

- Study questionnaire and Network enrollment questionnaire data will be linked using participant IDs.
- Contact information will be removed from the final merged dataset and data will be stored/saved using Unique Participant IDs.
- Data Analyses will be completed as described in Section 11.3 Final Analysis Plan.

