7 STUDY PROCEDURES/EVALUATIONS

Questionnaire Development

The study questionnaire was developed by the study team, and contains questions adapted from the United Kingdom's SCRIPT trial and previous Network studies. The questionnaire has undergone review by the NCC to ensure it is psychometrically sound and to ensure the data it collects will allow for adequate evaluation of study objectives. Further, cognitive testing of the questionnaire was completed, in which dentists reviewed their responses to a completed survey and were probed to assess possible respondent problems in understanding questions, recalling necessary information, and/or reporting accurately.

Questionnaire User Testing

The NCC will perform internal testing of the electronic study questionnaire, including internet browser compatibility. Study team members (e.g. SPI, National Network Director, Regional Directors, etc.) will be given the opportunity to externally test the website prior to administration to study participants.

Questionnaire Administration

According to the inclusion criteria, eligible participants, i.e., Network dentists and dental therapists whose practice includes non-implant restorative dentistry will be identified from their responses to the Network's enrollment questionnaire.

Consistent with regulations outlined by the University of Alabama IRB and regional/local IRBs, information about the study will be provided to all eligible participants via an information sheet/questionnaire link in the email invitation.

After the initial invitation and follow-up email reminders, the NCs will systematically contact non-responders, and participants with incomplete information, by email, phone, or fax to encourage questionnaire completion. If no feedback is received or the participant does not complete the questionnaire after these follow-up attempts, it will be assumed the practitioner is not interested in the study. Node Coordinators may also contact participants as part of data cleaning conducted by the NCC.

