11.2 Sample Size Considerations

The primary aim of the study is descriptive (i.e., to estimate the level of concordance with national guidelines in the sample overall as well as in selected subgroups). As such, sample size calculations are based on the precision with which we can estimate guideline concordance. To a good approximation, if W is the width of the 95% confidence interval (i.e., the confidence interval is of the form $P \pm W/2$) for an estimated proportion P based on N observations, then the N needed to achieve that width is given by

$$N = 16*P*(1-P) / (W^2)$$
,

where P and W are expressed on a fractional basis. Thus, a proportion of 20% corresponds to P=0.20, and if the width of the conf interval were 10 percentage points then W would be 0.10. For a given value of W, the formula above is symmetric about P=0.5 and is largest for P=0.5. Hence using P=0.5 above will give a conservative value of N that assures a width \leq W regardless of the value of P.

The target N of 385 chosen for this study will enable us to estimate proportions for the population as a whole with a precision (95% confidence interval) of no greater than \pm 5 percentage points, \pm 7.1 percentage points for subgroups of size N/2, \pm 8.7 percentage points for subgroups of size N/3, and \pm 10 percentage points for subgroups of size N/4.

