11.3 Final Analysis Plan

Primary Objective: Determine the extent to which, for permanent posterior teeth with deep occlusal caries extending to the inner 1/3 of dentin, Network dentists and dental therapists use caries removal strategies that are in concordance with the recommendations of the ICCC.

The primary analysis will be descriptive in nature. The source data for this analysis will be the proportion of the time dentists and dental therapists say they remove all caries at the periphery of the cavity and stop before the pulp is exposed ("selective caries removal"), which will be assessed separately for patients with symptomatic caries and for patients with asymptomatic caries. For each of these two subgroups, we will describe this as a continuous measure using either means and standard deviations (SD) or, if the data are markedly skewed, medians and interquartile ranges.

We will also calculate the percentage of dentists who are "concordant" with guidelines by dichotomizing this measure. Since there is no universally agreed upon definition for how to define concordance based on such data, we plan to use a variety of cut points to document the extent to which concordance varies with the choice of threshold used to define concordance. These cut points will range from a high of selective caries removal 75% of the time, which we feel is a reasonable measure of good concordance, to a low of selective caries removal 25% of the time to allow for comparison with some previous reports in the literature (15,21,22).

As a secondary analysis, we will use logistic regression analysis to determine the extent to which concordance varies according to selected provider characteristics. For the purposes of this analysis, we will define concordance using our upper end threshold of selective caries removal 75% of the time. We will initially look at all candidate variables in a univariate manner and will use those significant based on these analyses to conduct a reverse stepwise multiple logistic regression analysis. As before, separate analyses will be done for patients with symptomatic caries and for patients with asymptomatic caries.

An additional secondary analysis related to this objective will be to assess the relative importance of various factors when making clinical decisions about management of deep carious lesions. Each factor will be graded on a 5-point Likert scale and simple descriptive statistics will be used to summarize the information.

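### Strata are sampled at unequal rates and wave 2 sampling may change, but Section 11.3 names no weighting, so differences tied to enrollment-questionnaire (EQ) variables go uncorrected as written

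*Protocol*

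**What the plan says.** - **Sampling (Protocol Section 4).** "The study population will include a stratified random sample". All eligible practitioners in public health clinics, community health centers and VA services are invited; other practice types are sampled at random. After the first wave, "the study team will review the response rate based on EQ practitioner criteria, and may refine the sampling approach for wave 2 recruitment". The section gives no criterion or limit for the change and does not ask for the resulting selection probabilities to be kept.
- **Frame (Section 6.2).** "Eligible dentists and dental therapists will be identified from responses to the Network Enrollment Questionnaire". EQ data therefore exist for everyone invited, whether or not they answer.
- **Linkage (Section 6.3).** "Study questionnaire and Network enrollment questionnaire data will be linked using participant IDs". The section then sends the reader to Section 11.3 for the analyses.
- **Non-responders (Section 7).** After reminders and further contact by email, phone or fax, "it will be assumed the practitioner is not interested in the study".
- **Target (Section 11.2).** The aim is to "estimate the level of concordance with national guidelines in the sample overall as well as in selected subgroups". The section adds: "The target N of 385 chosen for this study will enable us to estimate proportions for the population as a whole", to within ±5 points. The objectives tables in Section 3 speak instead of participating practitioners, and the summary speaks of eligible ones.
- **Analysis (Section 11.3).** "The primary analysis will be descriptive in nature". It lists means with SDs or medians with interquartile ranges, and percent concordant at several cut points, separately for symptomatic and asymptomatic caries. A logistic regression on provider characteristics follows. No weights and no comparison of responders with non-responders are named. The missing-data paragraph covers incomplete questionnaires only.

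**The concern.** The design gives practitioners unequal chances of being invited and allows those chances to change between waves. Response may also differ by EQ characteristics; the planned review of response by EQ criteria shows that the team allows for this. A plain percentage over all respondents estimates the population value only if neither difference is related to the answer.

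Section 2.2 gives some reason to doubt that. It reports that younger dentists, female dentists and those working where guidelines were available tended to be more conservative in removing caries.

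Two results are exposed. One is overall concordance, which is the primary result. The other is the proportion willing to join a trial, which Section 11.3 makes one of three inputs to the decision whether a trial is warranted. Willingness is plausibly the more exposed of the two, since ignoring a research questionnaire may itself signal reluctance to join research. The regression in Section 11.3 describes associations and does not correct either overall figure.

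**Working it through.** **1. The plan's own precision figures.** With z = 1.96, P = 0.5 and half-width h = 0.05:

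N = z²P(1−P)/h² = 384.15, rounded up to 385.

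Half-widths at 385, 385/2, 385/3 and 385/4 are 4.99, 7.06, 8.65 and 9.99 points, which match the stated 5, 7.1, 8.7 and 10. (The printed formula with constant 16 gives 400, so 385 comes from z = 1.96.) All these figures assume simple random sampling, with no weighting and no non-response effect.

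**2. Inputs the protocol does not give.** It states no expected response rate, no response by EQ class, and no link between response and concordance. Everything in steps 3 and 4 is therefore an assumption made to show a range.

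**3. Bias of the unweighted percentage.** Take two EQ classes of equal size with concordance p₁, p₂ and response rates r₁, r₂. The bias is

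(r₁p₁ + r₂p₂)/(r₁ + r₂) − (p₁ + p₂)/2.

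Example for 60%/40% concordance and 40%/20% response: (0.24 + 0.08)/0.60 − 0.50 = 0.533 − 0.500 = 3.3 points.

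| Response r₁/r₂ | 55%/45% concordance | 60%/40% | 70%/30% |
|---|---|---|---|
| 30%/30% | 0 | 0 | 0 |
| 40%/30% | 0.7 | 1.4 | 2.9 |
| 40%/20% | 1.7 | 3.3 | 6.7 |
| 50%/20% | 2.1 | 4.3 | 8.6 |

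Entries are percentage points. Weighting the classes back to their share of the frame removes this bias; it does nothing for differences between responders and non-responders within a class.

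**4. Cost in precision.** With population shares W = 0.5 and respondent shares s, the design effect is the sum of W²/s. For 40%/20% response, s = 2/3 and 1/3, so it is 0.25/(2/3) + 0.25/(1/3) = 0.375 + 0.75 = 1.125. The half-width at 385 is 4.99 × √(design effect), and the N needed to hold ±5 is 384.15 × design effect.

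| Response | Design effect | Half-width at 385 | N for ±5 |
|---|---|---|---|
| 40%/30% | 1.02 | 5.05 | 393 |
| 40%/20% | 1.125 | 5.30 | 433 |
| 50%/20% | 1.225 | 5.53 | 471 |

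**5. What is not sized.** The effect of the census and sample strata, and of any wave 2 change, is left out of steps 3 and 4. It depends on each stratum's share of the frame at sampling, after the enrollment drive of Phase 1, and on its share of respondents. The protocol gives neither.

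**The case against.** The strongest objection is that this reads an unadjusted analysis into silence. A weighted percentage is also descriptive, the protocol never rules weights out, and Section 15.3 leaves the content of the final reports to a separate operating procedure that is not shown. That stands as far as it goes, and a reader should not infer that the sponsor has decided against weighting. But Section 6.3 names Section 11.3 as the plan the analyses will follow. The open wave 2 change is also a design element of the protocol itself. Inclusion probabilities have to be recorded when sampling takes place, and a later analysis document may be unable to rebuild them.

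Several stronger readings are not supported:

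- *That non-response bias is present.* It is zero if response is unrelated to the answer, and nothing in the protocol shows otherwise.
- *That the bias is 5 to 7 points.* A reader might take (1 − response rate) × difference with 30% to 50% response and a 10-point gap: 0.7 × 10 = 7 and 0.5 × 10 = 5. Both inputs are assumed, and the result is total bias, of which EQ weighting removes only a part.
- *That the wave 2 change is the only answer to non-response.* Section 7 plans reminders and contact by phone or fax, and Section 5.2 offers payment and recruitment meetings. A refined wave 2 might also improve balance.
- *That non-responders are excluded by an analysis rule.* The sentence in Section 7 ends contact attempts. It does not bar use of their EQ data.
- *That age, gender and region are available for weighting.* Section 5.1 names only EQ items 1, 7 and 21 and contact information; practice type is implied by the strata.

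**Conclusion.** The point holds in a limited form. With a census stratum, a sampled stratum and an open-ended wave 2 change, plain descriptive statistics do not support a precision claim for the whole population. Followed as written, the plan leaves any selection or response difference tied to EQ variables uncorrected.

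The size is unknown. For two equal EQ classes at 60%/40% concordance and response of 40%/30% to 50%/20%, the EQ-explained bias is about 1.4 to 4.3 points. It is zero at equal response, and it halves or doubles with a smaller (55%/45%) or larger (70%/30%) gap in concordance. Beside a ±5 margin that is enough to act on, but it is an illustration and not an estimate for this study.

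Weighting is a partial remedy. Bias within EQ classes remains. The last inclusion criterion is the first item of the study questionnaire (Section 5.1), so the eligibility of non-responders is unknown.

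**What to change.** 1. State one target population, and use it in the summary, Section 3 and Section 11.2.
2. In Section 4, require the inclusion probability of every invitee to be recorded by stratum and wave, and any wave 2 change to be documented before wave 2 invitations go out.
3. In Section 11.3, add a table comparing responders with non-responders on the EQ variables actually held.
4. Report overall concordance (symptomatic and asymptomatic) and willingness weighted for selection and for EQ-based response, beside the unweighted estimates, with the design effect. In the response adjustment, count practitioners who answer the first item and screen out as having responded.
5. For willingness, add a worst-case bound that counts every non-responder as unwilling. Label it a bound and not an estimate, because some non-responders would have been ineligible.
6. State that EQ weighting removes only the part of the bias explained by EQ variables.

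The cost is record keeping at sampling and analysis time on data the coordinating center already uses to select invitees, plus some precision. Under the assumptions above, the half-width goes from 4.99 to between 5.05 and 5.53 points at 385 respondents. Holding ±5 would take about 393 to 471 respondents, before any further effect of the stratum weights.
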